9.2.3 IV iron use every 4 weeks during the treatment period

The IV iron use every 4 weeks during the treatment period will be calculated for monthly intervals. The treatment period will be divided into 28 days and the monthly mean of IV iron for each period will be calculated using the following formula:

Monthly iron use for each subject = total IV iron in mg / [(last dose date – first dose date of IV Iron in the period +1)/ 28]

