3.2.2. Exploratory Endpoints/Analyses

The additional exploratory endpoints in this study are:

- Time to first RBC transfusion
- Proportion of patient with a mean Hb levels ≥10 g/dL in the first 8 weeks after conversion
- Proportion of patient with a mean Hb level ≥10 g/dL based on baseline ESA use status (≥ 6 weeks and < 6 weeks)
- Evaluate the utilization of intravenous (IV) iron (IV iron use/4 weeks)
- Evaluate the effect on iron indices
- Evaluate dosing adherence
- Conversion subjects:
 - o Comparison of starting dose of roxadustat to roxadustat dose at Week 16-24
- Mean number of dose adjustments during study

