4.7.2.2. Intravenous (IV) Iron Supplementation

Intravenous iron should be considered for subjects with ferritin < 100ng/mL or TSAT <20%. IV iron should be administered in 5 doses of 50 mg/dose. Medical Monitor should be contacted if more IV iron is required.

In addition to scheduled assessments (Appendix 2: Table 4), iron indices may be assessed anytime (via central lab) to evaluate iron storage status of the subjects, if considered necessary by the Investigator.

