1 INTRODUCTION

This statistical analysis plan (SAP) provides a more technical and detailed elaboration of the statistical analyses of efficacy and safety as outlined and/or specified in the final study protocol. Specifications of tables, figures, and data listings are contained in a separate document.

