4.2 EXPLORATORY ENDPOINTS

- Proportion of subjects with a mean Hb level within 10-12 g/dL from Week 16 to Week 24
- Proportion of subjects with Hb > 12 g/dL any time during treatment
- Proportion of subjects with Hb > 13 g/dL any time during treatment
- Percentage of time with Hb, values within 10.0 to 12.0 g/dL from Week 16 to Week 24
- Time to first RBC transfusion
- Proportion of subjects with a mean Hb level ≥ 10 g/dL in the first 8 weeks after conversion or initiation of treatment
- Proportion of subjects with a mean Hb level ≥ 10 g/dL (averaged from Week 16 to Week 24) based on baseline ESA use status ≥ 6 weeks (conversion from ESA to roxadustat based on prior ESA use) and < 6 weeks (initiation of roxadustat based on body weight)
- Evaluate the utilization of IV iron (IV iron use/4 weeks)

- Evaluate the effect on iron indices
- Evaluate dosing adherence
- Conversion subjects: Comparison of starting dose of roxadustat to roxadustat dose at Weeks 16 to 24
- Mean number of dose adjustments (including dose-hold) during study
- Proportion of subjects requiring blood/pRBC transfusion from Week 5 (Day 29) to Week 24/ET.
- Proportion of subjects requiring rescue therapy (blood/pRBC transfusion or ESA rescue) from Week 5 (Day 29) to Week 24/ET

In addition to the exploratory endpoints in the protocol, additional exploratory efficacy endpoints of interest are presented in this section.

RBC transfusion data is collected in the Blood Transfusions form of the eCRF.

For efficacy evaluation, Hb values will be censored for 4 weeks if blood/pRBC is administered during the treatment period. Hb results obtained from the central laboratory will be used to determine the Hb response.

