5.4 ADDITIONAL DATA HANDLING RULES AND PRESENTATION SPECIFICATIONS

The following general guidelines will apply to all statistical analyses and data presentations:

- Baseline is defined as the last available value obtained prior to the first dose of study drug, unless otherwise specified in this SAP.
- Hb baseline is defined as the mean of available values obtained during screening prior to the first dose (including pre-dose Day 1 Hb value).

- Baselines for reticulocyte count, reticulocyte hemoglobin content (CHr), serum iron parameters (transferrin, TIBC, TSAT, ferritin, sTfR, and iron) are defined as the values obtained on Day 1 (excluding screening) prior to the first dose.
- Baselines for blood pressure and heart rate are defined as the mean of values obtained during screening (including Day 1) prior to the first dose.
- Unscheduled visits within an allowable window will be grouped into the closest scheduled visits based on the visit window specified in [Appendix 1](#). For subjects who have more than one measurement at a certain scheduled visit, the last measurements will be used, with the exception of CPK, WBC, liver function tests (i.e., ALT, AST, GGT, ALP, and total bilirubin), in which the maximum measurement will be used.
- By default, US conventional units will be used for laboratory value presentations. A separate set of laboratory tables with SI units may be required by regulators, such as the European Medicines Agency (EMA).
- Age is calculated as of date that the informed consent form was signed.
 - age = INTCK('YEAR', Birth date, date of Informed Consent, 'C') where INTCK is a SAS function.
- Duration of treatment or days on treatment is calculated as: last dose date – first dose date +1
- Body weight, height and temperatures will be converted using the following formulas:
 - kg = lb/2.2
 - cm = 2.54 x in
 - C° = (5/9) x (F° – 32)
- Mean Arterial Pressure (MAP) will be calculated for each subject using the following formula: MAP = (2/3) * diastolic blood pressure + (1/3) * systolic blood pressure.
- All percentages will be rounded to one decimal place and lined up by the decimal place. The percentage will be suppressed when the count is zero.
- All tables and listings will have a header showing “FibroGen, Inc.”, the protocol number, and the page number. Footer will indicate the program file path/name, run date and run time.

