6 SUBJECT ACCOUNTABILITY AND DISPOSITION

The following subject data will be summarized and presented if applicable, by number and percentage:

- Subjects enrolled at each center, and for all centers combined (using the enrolled population)
- Subjects in each analysis set (using the enrolled population)
- Subjects who prematurely discontinued during the treatment period, and by discontinuation reason for the enrolled population.
- Subjects who complete the treatment period (will be considered as “completers”)
- Subjects who participated in the Post-treatment Follow-Up
- Subjects who completed the EOS Visit
- Subjects who entered extension study

Kaplan-Meier plots will be generated for premature treatment discontinuations showing one curve.

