9.2.1 Time to first RBC Transfusion

For a subject receiving a RBC transfusion, the Time at Risk (time up to first RBC transfusion) will be calculated (in weeks) as:

$$(\text{First RBC transfusion date} - \text{First dose date of study medication} + 1) / 7$$

For a subject not receiving a transfusion, the Time at Risk (time until they get censored) is calculated as:

$$(\text{Date of last study visit} - \text{First dose date of study medication} + 1) / 7$$

Subjects with no events were censored at the date of minimum (last dose date, last visit date, death date, Week 24*7).

Time to first RBC transfusion will be analyzed using the Kaplan-Meier method with KM curve plotted to derive the following:

- Proportion of subjects with any RBC transfusion up to Week 24

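### The formula for IV iron per 4 weeks starts its clock at the first iron dose, so the value depends on iron timing, and subjects without IV iron have no defined value

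*SAP*

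**What the plan says.** Both documents list the endpoint as exploratory: "Evaluate the utilization of intravenous (IV) iron (IV iron use/4 weeks" (Protocol 3.2.2) and "Evaluate the utilization of IV iron (IV iron use/4 weeks" (SAP 4.2). SAP 9.2 places the exploratory analyses in the full analysis set, which is not restricted to subjects who receive iron.

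SAP 9.2.3 divides treatment into 28-day periods and gives the per-subject value for each period as "total IV iron in mg / [(last dose date – first dose date of IV Iron in the period +1)/ 28", followed by a closing bracket. It does not say whether the last dose is of study drug or of iron, and it gives no value for a subject or period without IV iron.

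Elsewhere the SAP has a time-on-treatment quantity. Section 5.4 states: "Duration of treatment or days on treatment is calculated as: last dose date – first dose date +1". Section 9.2.3 does not use it.

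On the amount of iron, Protocol 4.7.2.2 says "IV iron should be administered in 5 doses of 50 mg/dose", without an interval between doses. IV iron is to be considered only when ferritin is below 100 ng/mL or TSAT is below 20%, so periods without iron are to be expected.

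**The concern.** A rate per 4 weeks needs the time during which the subject could have received iron as its denominator. Here the denominator starts when iron starts. Two subjects with the same milligrams and the same time on treatment can therefore get different values, and less iron can score higher than more. Subjects without iron, who should pull the mean down, have no start date and drop out if the formula is applied literally.

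IV iron utilization is a stated objective (Protocol 3.1.2, SAP 3.2), and Protocol 4.7.2 points to reduced IV iron need in earlier studies. SAP 11 also allows iron supplementation data to be split by dialysis organization. If organizations space iron doses differently, the formula could show a difference in use where the milligrams are equal.

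**Working it through.** The plan states no numerical result for this endpoint, so there is no figure to reproduce. The check evaluates the formula directly.

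**Inputs.** Dose 50 mg and course 5 × 50 = 250 mg (Protocol 4.7.2.2). Period 28 days (SAP 9.2.3). Treatment 24 × 7 = 168 days, which is 6 × 28. Assumption: iron is given at consecutive dialysis sessions on Days 1, 3 and 5 of each week. Unless stated otherwise, the subject is on study drug for the whole period. The correct value is then simply the milligrams given in the period.

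**Reading A: both dates are IV iron dates.** Value = mg / [(last iron day − first iron day + 1)/28].
- Days 1, 3, 5, 8, 10: 250/(10/28) = 700.
- Days 5, 8, 10, 12, 15: 250/(11/28) = 636.4.
- Any single dose: 50/(1/28) = 1,400. One fifth of the iron scores twice as high as the 10-day course.
- A course on Days 19, 22, 24, 26, 29 crosses into the next period: 200/(8/28) = 700 in period 1 and 50/(1/28) = 1,400 in period 2.

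A period has 12 possible start sessions. Starts 1 to 8 keep all five doses inside it. Starts 9 to 12 split 4+1, 3+2, 2+3 and 1+4. So 4 of 12 cross the boundary and 2 of 12 leave a single dose in one period, without any incomplete course.

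**Reading B: the last date is the last study-drug dose in the period (Day 28).** Value = mg / [(28 − first iron day + 1)/28].

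| First iron day | Denominator | One 50 mg dose | 250 mg course |
|---|---|---|---|
| 1 | 28/28 | 50 | 250 |
| 8 | 21/28 | 66.7 | 333.3 |
| 15 | 14/28 | 100 | 500 |
| 22 | 7/28 | 200 | crosses the boundary |
| 28 | 1/28 | 1,400 | crosses the boundary |

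Only a Day 1 start is correct. If study drug stops before the first iron dose of the period, the denominator fails: stop Day 14 and iron Day 15 give (14 − 15 + 1)/28 = 0; stop Day 10 gives −4/28.

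If the last study-drug date is not confined to the period, timing still drives the value. For a subject treated to Day 168, 250 mg starting on Day 1 scores 250/(168/28) = 41.7, and starting on Day 141 it scores 250/(28/28) = 250.

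**Non-users.** With no first iron date the denominator is undefined. Suppose 10%, 30% or 50% of subjects (assumed) receive one 250 mg course in a period.
- Mean with non-users at 0: 250 × 0.10, 0.30, 0.50 = 25, 75, 125 mg.
- Leaving out non-users alone: 250/25, 250/75, 250/125 = 10, 3.3, 2 times.
- Users only under Reading B with a Day 15 start: 500/25, 500/75, 500/125 = 20, 6.7, 4 times.
- Users only under Reading A with a 10-day course: 700/25, 700/75, 700/125 = 28, 9.3, 5.6 times.

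**The case against.** Four points can be made for the plan.

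1. Where the SAP uses the last dose date without qualification (5.4, 8.1, 9.2.1, 13.2.8), it means study drug. That favors Reading B, under which inflation is at most 2 times when iron starts by Day 15. This is fair, and Reading A should not be taken as settled. But the wording can be read either way, and under B the value still moves with iron timing.

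2. The mention of iron in the denominator may be a misplaced phrase. Without it, the line would resemble the time-on-treatment form in SAP 5.4, and non-users would score 0 because their numerator is 0. That is plausible, but it is inference. The text as written still needs correcting.

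3. The SAP does not plan a users-only mean. It specifies a value for each subject in the full analysis set, and "Specifications of tables, figures, and data listings are contained in a separate document" (SAP 1), which may set non-users to 0. This also stands: the fault is a missing rule, and the 28-fold figure stacks Reading A, an assumed schedule, an assumed 10% user share and an assumed exclusion. A display rule in that separate document would not repair the denominator.

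4. The endpoint is exploratory and SAP 11 states that no hypothesis is tested. This limits the consequence but does not make the formula right.

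**Conclusion.** The concern holds. Under either reading, the result is not milligrams per 4 weeks on treatment regardless of when iron was given. For a subject treated throughout the period, with both dates confined to it, the denominator cannot exceed 28 days. The error can then only raise the reported use, and averaging does not cancel it. A 250 mg course scores 636 to 700 mg under Reading A when it falls within one period, and 250 to 500 mg under Reading B for starts from Day 1 to Day 15. A single 50 mg dose scores 1,400 mg under A and 50 to 1,400 mg under B.

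The value for subjects without iron is undefined in the SAP. The size of that effect depends on the share of users, which the documents do not give. All sizes rest on assumed dosing days. The consequence is confined to one descriptive exploratory endpoint; the hemoglobin endpoints do not use this formula. It should be corrected because the reported figure could be several times the iron actually given.

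**What to change.** Keep the per-subject, per-period quantity and replace the denominator:

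IV iron per 4 weeks = total IV iron (mg) dated within the subject's days on study treatment in the period / (those days / 28).

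- Count periods from Day 1, which is the first study-drug date (SAP Table 5), and cut at Day 168. This matches the limit in SAP 9.2.1: "Subjects with no events were censored at the date of minimum (last dose date, last visit date, death date, Week 24*7". State that the scheduled Week 24 day, Day 169 in Table 5, falls outside the cut.
- In each period, count days from its first day to the earlier of its last day and the last study-drug dose.
- Score a subject on treatment without IV iron in the period as 0, and report the n in each mean.
- Add a rule for short last periods. SAP 6 expects early stops, since it tabulates "Subjects who prematurely discontinued during the treatment period, and by discontinuation reason for the enrolled population". With the corrected formula, one 50 mg dose scores 50/(2/28) = 700 with 2 days on treatment, 50/(7/28) = 200 with 7 and 50/(14/28) = 100 with 14. Either prespecify a minimum number of days for a period to count, or also report the pooled rate: total mg / total days on treatment × 28.

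A fully treated subject given 250 mg in a period then scores 250 whatever the iron dates, and a non-user scores 0. The cost is one SAP formula and its programming, with no new data and no change to how iron is given.

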9.2.4 Iron indices

The mean change from baseline in the following endpoints will be summarized and data up to the Week 24 visit will be included in the analyses:

- Value and change from baseline in CHr at each of the selected time points (e.g., Weeks 8, 16, 24)
- Value and change from baseline in serum ferritin at each of the selected time points, total and sub-grouped by baseline values of <100 ng/mL, 100 to <400 ng/mL and ≥ 400 ng/mL.
- Value and change from baseline in TSAT at each of the selected time points, total and sub-grouped by baseline values of $<20\%$, 20% to $<40\%$, and $\geq 40\%$.
- Value and change from baseline in serum iron at each of the time points tested
- Proportion of patients with CHr $>$ ULN at each time point tested: Weeks 8, 16, 24

9.2.5 Dosing adherence

See SAP [section 8.1.2](#) Treatment Compliance

9.2.6 Comparison of starting dose to Weeks 16 to 24 dose

For proportion of patients with dose increased, dose decreased, and dose not changed, an analysis will be done comparing starting dose to average prescribed dose over Weeks 16 to 24.

9.2.7 Dosing adjustments

See SAP [section 8.1.1](#) Dosing Changes

9.2.8 Blood Transfusion and ESA Usage as Rescue Therapy

Blood/pRBC transfusions will be recorded in the Blood Transfusion Form of the eCRF. ESA, as rescue therapy, will be recorded in the Concomitant Medication eCRF.

The following 2 endpoints will be analyzed:

- Proportion of patients requiring a blood/pRBC transfusion from Week 5 (Day 29) to Week 24/ET. The 95% CI of the response rate will be presented based on normal approximation.
- Proportion of patients requiring rescue therapy (blood/pRBC transfusion or ESA rescue) from Week 5 (Day 29) to Week 24/ET. The 95% CI of the response rate will be presented based on normal approximation.

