Additionally, some patients are hyporesponsive to ESA therapy. A significant proportion (~ 17%) of DD-CKD patients require stable ESA dosing at 2 to 6 times the median seen in the entire CKD population (150 to 450 U/kg of IV epoetin TIW). This "hyporesponder" patient population accounts for approximately 50% of epoetin alfa consumption in the US (Besarab et al., 2009). This is a significant economic burden, and as noted above, higher doses of ESAs have been associated with higher rates of morbidity and mortality (Zhang et al., 2004; Unger, 2007; Szczech, 2008). Thus, this patient population has the greatest need for an effective and safe therapy for anemia. In turn, the increasing perception that high ESA dosing is associated with significant risk, especially in patients not achieving target, is expected to lead to lower ESA dosing and an associated higher prevalence of patients with low Hb levels. In December of 2007, 2.1% of patients had Hb levels < 9 g/dL, 7% had Hb levels < 10 g/dL, and 21.6% did not reach 11 g/dL, while 34.8% were 11 to 12 g/dL (USRDS, 2009). Hb levels < 11 g/dL in this population are associated with increased mortality and hospitalization rates, and failure to achieve a Hb level > 11 g/dL is a prognostic indicator of poor outcomes (Ma, 1999; Regidor, 2006). In patients with persistently low Hb levels, mortality risk is strongly associated with the patient's ability to achieve a hematopoietic response (Bradbury, 2009). Additionally, ESA therapy for anemia in patients with ESRD on HD usually requires concomitant IV iron supplementation to avoid functional iron deficiency and epoetin dose escalation; however; IV iron use is not without risk. However, as reported by the USRDS (USRDS, 2013), administration of IV iron is at an all-time high. Among patients on HD, the transfusion rate, at 2.7% to 2.9% at the beginning of 2010, reached 3.3–3.8 percent in the first six months of 2012. Among patients on PD, the rate has increased from 2.3–2.9 to 3.0–3.9.

There is currently an unmet medical need for an oral treatment that can correct anemia in patients with NDD-CKD and DD-CKD while avoiding supraphysiologic levels of circulating plasma EPO levels.

Roxadustat is an oral medication that could potentially deliver effective treatment for CKD-related anemia with less need for IV iron supplementation and without producing supraphysiologic levels of

Confidential Page 23 of 69

[figure not shown]

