9.3. Analysis of the Efficacy Endpoints

The efficacy endpoint will be evaluated using the proportion (%) of subjects with mean value of Hb measurements of Week 16-Week $24 \ge 10$ g/dL.

The 95% CI of the response rate will be presented based on the exact method of Clopper-Pearson.

For efficacy analysis, a multiple imputation (MI) method will be used. This will be implemented on the raw Hb values, then the Hb-relates endpoint summaries will be derived based on the imputed data (algorithm as used for the previous phase 3 studies).

For continuous endpoints, changes from baseline will be presented descriptively. Missing Hb values will be imputed using a multiple imputation procedure.

Proportion of responders will be presented descriptively with count and percentages and 95% confidence interval of the responder rate.

Time to response will be analyzed using the Kaplan-Meier method with KM curve plotted.

Protocol FGCL-4592-096 A01

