9.2 ANALYSIS OF EXPLORATORY ENDPOINTS

The analysis for the exploratory endpoints will be based on the FAS population.

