11 INTERIM ANALYSIS

An interim analysis may be performed to report topline results at the Sponsor's discretion. Since no statistical hypothesis testing is performed for this study, no multiplicity adjustment is required.

For better execution and understanding, certain data points (e.g., data linked to dose adjustments, iron supplementation, etc.) may be analyzed by patients participating under each dialysis organization (i.e., all patients, patients from DaVita, and patients from USRC), as needed.

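### SAP 9.2.8's normal-approximation interval puts the upper limit for transfusion and rescue too low if events are few (minor)

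*SAP*

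**What the plan says.** SAP 9.2.8 defines two proportions over the window from Day 29 to Week 24 or early termination: subjects needing a transfusion, and subjects needing a transfusion or ESA rescue. The first bullet reads, in part: "blood/pRBC transfusion from Week 5 (Day 29) to Week 24/ET. The 95% CI of the response rate will be presented based on normal approximation". The second bullet ends with the same instruction: "The 95% CI of the response rate will be presented based on normal approximation". There is no continuity correction, no truncation at zero and no rule for few or no events.

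Both endpoints are SAP additions. Protocol 3.2.2 lists time to first transfusion but neither proportion, and SAP 4.2 states: "In addition to the exploratory endpoints in the protocol, additional exploratory efficacy endpoints of interest are presented in this section". The denominator comes from SAP 9.2: "The analysis for the exploratory endpoints will be based on the FAS population". SAP 5.1 makes intervals two-sided 95% by default, and SAP 5.2 plans about 300 subjects.

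Transfusion is also covered by the Kaplan-Meier analysis in SAP 9.2.1, which yields "Proportion of subjects with any RBC transfusion up to Week 24", counted from first dose rather than from Day 29. The composite has no second analysis.

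**The concern.** The Wald interval is centred on the observed proportion and takes its width from that proportion's estimated standard error. When the proportion is small, the estimate is right-skewed. Samples that happen to show few events give both a low centre and a narrow interval, so misses concentrate on one side, with the upper limit below the truth.

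That is the side that matters here. A reader of a rescue endpoint wants to know how high the true need for transfusion or ESA could be, and the interval would understate it.

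There is no technical reason to accept this. For the Hb responder rate, SAP 9.1.1 pools estimates and standard errors over 200 imputed datasets, which calls for a standard-error-based interval. The SAP 9.2.8 endpoints are plain counts over n, so a binomial interval applies directly.

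**Working it through.** **Inputs.** n = 300 (SAP 5.2); the FAS may be smaller. Two-sided 95%, z = 1.96 (SAP 5.1). No expected rate for either endpoint appears in either document, so true rates of 2-5% are an assumption. The only background figures are in Protocol 2.2: "Among patients on HD, the transfusion rate, at 2.7% to 2.9% at the beginning of 2010", rising to 3.3-3.8% in the first half of 2012, with no time unit.

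**The plan's own figure.** SAP 9.2.8 states none. The only interval figure is the 9.5% width for an 80% Hb response at n = 300 (SAP 5.2). Plain Wald gives 2 × 1.96 × √(0.8 × 0.2/300) = 9.05%, Clopper-Pearson 9.36%, and Wald with continuity correction 9.39%. That figure concerns a different endpoint and is not used below.

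**Formulas.** Wald: p ± z√(p(1−p)/n). Clopper-Pearson: beta quantiles, lower limit Beta(0.025; x, n−x+1), upper limit Beta(0.975; x+1, n−x). Wilson: the score interval.

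**One worked case, 9/300.** p = 0.03, SE = √(0.03 × 0.97/300) = 0.00985, 1.96 × SE = 1.93 points. Wald 1.07-4.93%; Clopper-Pearson 1.38-5.62%; Wilson 1.59-5.60%. The Wald upper limit is 5.62 − 4.93 = 0.69 points below the exact one.

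**Coverage.** Exact binomial enumeration at n = 300, true rate in steps of 0.0001:

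| True rate | Method | Coverage min / mean / max | Upper limit below truth (mean) |
|---|---|---|---|
| 2-5% | Wald | 87.7 / 92.8 / 95.3% | 6.3% |
| 2-5% | Clopper-Pearson | 95.1 / 96.6 / 98.1% | 1.6% |
| 2-5% | Wilson | 93.7 / 95.2 / 96.9% | 1.6% |
| 2.7-3.8% | Wald | 90.1 / 92.6 / 95.3% | 6.5% |
| 5-10% | Wald | 92.0 / 94.0 / 95.4% | 4.7% |
| 12-16% | Wald | 93.4 / 94.5 / 95.4% | 3.8% |

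At n = 270 (assumption) mean Wald coverage over 2-5% is about 92.6%, so a somewhat smaller FAS changes little.

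**Expected gap, exact minus Wald upper limit:** 0.73 points at 2%, 0.69 at 3%, 0.65 at 5%, 0.55 at 12%, 0.50 at 16%.

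**Two readings of the background figures.**
- As cumulative risk over the window, they give 300 × 0.027 = 8.1 to 300 × 0.038 = 11.4 events, which is the 2.7-3.8% row.
- As a constant monthly risk m (assumption): SAP 13.2.1 places Week 24 at day 7 × 24 + 1 = 169, so the window is 169 − 29 = 140 days. Then 1 − (1 − m)^(140/30) is 12.0% at m = 2.7% and 16.5% at m = 3.8%. This is roughly the last row.

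**Degenerate cases.** At 0 events Wald gives 0-0% (exact 0-1.22%). The lower limit is negative when 0 < x < nz²/(n + z²) = 300 × 3.84/303.84 = 3.79, that is at 1, 2 and 3 events: −0.32%, −0.25% and −0.13%. The chance of 0-3 events is 14.9% at a true rate of 2%, 3.8% at 2.7%, 2.0% at 3% and 0.3% at 3.8%.

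**The composite.** It includes every transfusion, so its rate is at least as high and its expected gap no larger over the rates examined. Coverage does not follow the same order: it is 94.7% at 4% but 91.6% at 4.5%.

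**The case against.** The strongest reply is that nothing depends on this interval. The endpoints are exploratory, SAP 11 states "Since no statistical hypothesis testing is performed for this study, no multiplicity adjustment is required", and SAP 9.2.8 sets no threshold. The count and percentage are unaffected, and a reader with x and n can compute an exact interval. The shortfall is about 0.7 points even in the unfavourable range, and the event rate is unknown. All of that stands, and it keeps the point minor. It does not make the interval right: with no test, the interval is the main statement of uncertainty, and the composite has no other planned one.

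A second reply is that early terminators who leave event-free stay in the denominator, which could bias the proportion downwards by more than 0.7 points. That may be so; the documents give no dropout figure. It is a separate matter that no choice of binomial interval settles.

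Three stronger readings are tempting, and the documents do not support them.
- A reader might infer that SAP 9.2.8 contradicts the protocol, since Protocol 9.3 says "The 95% CI of the response rate will be presented based on the exact method of Clopper-Pearson". That sentence concerns the Hb response rate, and these two proportions are not protocol endpoints.
- A reader might expect a zero-width interval or a negative lower limit in the report. At n = 300 and rates of 2.7-3.8%, 0-3 events has a chance of only 3.8% to 0.3%.
- A reader might assume that the composite, having more events, is safely covered. Wald coverage is not monotone in the true rate, so that does not follow.

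**Conclusion.** The point holds, conditionally, and is minor. If the true proportions are around 2-5%, the planned upper limit misses low about two and a half times as often as it should (6.3/2.5), and two-sided coverage averages about two points under nominal. If they are around 12-16%, mean coverage is within half a point of nominal. The documents do not say which case applies: they give no expected rate for either endpoint, and the background figures carry no time unit and describe haemodialysis patients in general.

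The coverage figures assume plain Wald without continuity correction, about 300 subjects in the FAS, and every subject counted as a simple yes or no.

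**What to change.** In each of the two bullets of SAP 9.2.8, replace the reference to the normal approximation with the Wilson method or with the exact Clopper-Pearson method. Settle the choice before the results are seen.

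The cost is a change of wording in two places and one binomial option in PROC FREQ. Either method gives asymmetric intervals with a slightly higher upper limit. Over 2-5%, Clopper-Pearson is conservative (mean coverage 96.6%). Wilson is close to nominal (95.2%), but its lower limit lies above the truth 3.2% of the time. Since the upper limit is the one of interest and both methods miss there equally often (1.6%), either is acceptable.

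This corrects binomial coverage only. How subjects with incomplete follow-up before Week 24 enter the proportion needs its own statement.
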